4.4. Exclusion criteria

- Children and teenagers below the age of 18.
- Adults aged >35 years old.
- Patients with clinical and ultrasonographic diagnosis of acute HMC injury Type 3b who got injured more than seven days before potential enrollment into this study.
- Patients with clinical and ultrasonographic diagnosis of acute HMC injury Type 3A or Type 4.
- Bilateral acute HMC injury (Types 3A, 3B or 4).
- Proven or suspected HMC injury (Types 3A, 3B or 4) of the same lower limb in the time period of six months before potential enrollment into this study.
- Muscle injury caused by external impact on the back of the affected thigh (Category B according to Müller-Wohlfahrt et al., 2013).
- Surgery on the affected lower limb in the time period of one year before potential enrollment into this study.
- Acute or chronic lumbar pathology (because some cases of thigh pain may relate to spinal pathology; c.f. Linklater et al., 2010).
- No willingness of the patient to participate in this study, and/or written informed consent not signed and not personally dated by the patient.
- Contraindications of rESWT:
 - treatment of pregnant patients,
 - treatment of patients with blood-clotting disorders (including local thrombosis),

- treatment of patients treated with oral anticoagulants,
- treatment of patients with local bacterial and/or viral infections/inflammations,
- treatment of patients with local tumors, and
- treatment of patients treated with local corticosteroid applications in the time period of six weeks before the first rESWT session (if applicable).

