free recovery and the time to return to play by approximately three weeks without any significant increase in the risk of reinjury. However, it is not known whether starting rehabilitation already two days after injury has any benefit over starting rehabilitation five days after injury. We will therefore follow the recommendation by Jarvinen et al. (2017) and progress to the sub-acute phase after five days.

The criterion for progression to the subacute/regeneration phase will be

- absence of pain five days after injury.

If the symptoms caused by the injured muscle persist for more than five days we will reconsider the existence of more extensive tissue damage and/or intramuscular hematoma that might require special attention and treatment by an orthopedic surgeon.

Subacute/Regeneration Phase

The goals of the subacute/regeneration phase include:

- improve overall core stability,
- improve strength and symmetry,
- reduce pain during prone isometric, isolated hamstring contractions at 15° knee flexion,
- improve hamstring flexibility of both legs,
- improve hip flexor flexibility of both legs, and
- improve neuromuscular control.

During the subacute/regeneration phase the subject will work on both legs daily during a single session. Exercises will be conducted to correct the different risk factors and mechanisms related to the lesion of the hamstring musculature. The exercises will be divided into four groups:

- core stability and lumbopelvic control,
- flexibility and neural mobilization,
- hamstring and gluteal strength, and
- running technique

(see also

http://wolterskluwer.http.internapcdn.net/wolterskluwer_vitalstream_com/MP4s/permalink/ms/a/mss_2017_02_28_mendiguchia_msse-d-16-00910r4_sdc1.mp4).

In addition, basic aerobic conditioning will start when the subject will be able to perform at least three sessions of the running technique without any discomfort or pain. Three running sessions per week will be performed at the clinic of the Principal Investigator and will include four sets of five minutes at a low to moderate intensity (individually rated by the subject). Suspension of running sessions will be permitted in the event of discomfort or pain.

The criteria for progression to the functional phase will be:

- no pain in prone position with knee flexed to 15°,
- no pain during slump test,
- < 10% asymmetry when in prone position with knee flexed to 15°,
- < 10% asymmetry during active knee extension test, and

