4.9. Study treatment and visits

As outlined in Section 4.5 “Groups and treatments” above all subjects will perform RP that will last for eight weeks, independent of the individual time interval to return to play.

- The RP will start with a first visit to the clinic of the Principal Investigator during which clinical and ultrasonographic diagnosis will be performed. This first visit may take place on the day of injury (D0) or the first day (D1) or second day (D2) after injury (the sooner the better).
- After the first visit an individual number of days will follow until the fifth day after injury (D5) will be reached (acute phase). During this time the subject will apply the RICE principle (rest, ice, compression and elevation). Visits to the clinic of the Principal Investigator may be scheduled during this time but are not mandatory.
- On D5 the subacute/regeneration phase of the RP will start, with three visits per week to the clinic of the Principal Investigator (outlined in detail in Section 4.5 “Groups and treatments” above). The exact time for progression from the subacute/regeneration phase to the functional phase of the RP will be individually determined, depending on whether the criteria for progression will be fulfilled. During the functional phase there will also be three visits per week to the clinic of the Principal Investigator.
- Study treatments (rESWT or sham-rESWT) will start on D5. Each subject will be treated with nine sessions of rESWT or sham-rESWT, with three sessions per week. Accordingly, study treatments may take place at D5, D7, D9, D12, D14, D16, D19, D21 and D23.
- Six months after inclusion into the study there will be a separate visit for evaluating patient's satisfaction with the treatment outcome.

The time interval necessary for reaching return to play will be as follows:

- Based on our experience we expect that approximately 75% of the subjects treated with rESWT + RP will reach return to play within five weeks after D0.
- Furthermore, we expect that only approximately 25% of the patients treated with sham-rESWT + RP will reach return to play within five weeks after D0.

The Principal Investigator will perform the following procedures at the first visit:

- check eligibility
- obtain informed consent
- perform randomization
- collect patient's demographics & medical history

Furthermore, the Principal Investigator will perform the following procedures at all visits:

- record any concomitant medication

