4.11. Blinding of therapists and assessors

- Therapists applying the treatments will not be blinded. This will be done because even when using coded "active" and "placebo" handpieces in a study on rESWT, blinding of therapists can only be achieved when another person prepares the device before rESWT or sham-rESWT. This, however, is almost impracticable and has not been done in any of the more than 100 studies on radial and focused ESWT listed in the PEDro database (Schmitz et al., 2015). The solution to this issue is a strict, standardized way of interaction between the therapist and the patients, irrespective of treatment allocation (as mentioned in a study by Buchbinder et al., 2002). This approach will also be applied in the present study.
- All assessments before the first treatment (baseline) and during the follow-up period will be performed by assessors blind to the intervention.

5. Follow-up and statistical analysis

- Follow-up will be the same for all study patients (outlined in detail in Section 4.10. above).
- The design of this study guarantees that there will be full compliance with the allocated treatment and, thus, no contamination of one group.

- The patient's age, gender, body mass index, sport that practices, position in the field, sporting gesture that caused the injury are potential confounding factors when treating acute HMC injury Type 3b with rESWT. Normal distribution of these data will be tested using the D'Agostino-Pearson omnibus test. In case of passing the normality test we will report mean and standard error of the mean of these variables; otherwise we will report inter-quartile ranges of these variables. Comparison between groups will be performed with Student's t test in case of passing the normality test or the nonparametric Mann-Whitney test in case of not passing the normality test.
- As outlined in Section 4.11.1. "Primary clinical outcome and definition of treatment success" above, the primary clinical outcome will be the individual time (days) necessary to return to play. The primary clinical outcome will return a single data point (number of days) for each patient. Time of return to play is not normally distributed data. Accordingly, we will report inter-quartile ranges of this variable. Comparison between groups will be performed using the nonparametric Mann-Whitney test.

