5.1. Power analysis

In the aforementioned studies by Reurink et al. (2014a) (outlined in detail in Fig. 5 above) and Bayer et al. (2017) (outlined in Fig. 6 above) the cumulative probability of resumptions of sports activity on day 35 after acute HMC injury Type 3b in professional soccer players (Reurink et al., 2014a) or recreational athletes (Bayer et al., 2017) was only respectively 20% (Reurink et al., 2014a) or 5% (Bayer et al., 2017) after treatment with a rehabilitation program (Fig. 9).

On this basis we performed a Power analysis for a percentage of 25% as well as (ii) for various other percentages (ranging between 10% and 99.9%) of patients with treatment success when treated with sham-rESWT + RP (n=20), accounting for a two sided-confidence interval of 95% (and, thus, a type-1 error rate of 5%) and a percentage of patients with treatment success when treated with rESWT + RP (n=20) of 75%. Calculations were performed using the software, Open Source Epidemiologic Statistics for Public Health (www.openepi.com). The results are summarized in Table 3 (on the next page).

Furthermore, we calculated the minimum sample size in both groups (rESWT + RP, sham-rESWT + RP) that would be necessary for detecting a difference in treatment success between the patients treated with rESWT + RP and the patients treated with sham-rESWT + RP accounting for a two sided-confidence interval of 95% and a power of 0.8. Calculations were also performed using the software, Open Source Epidemiologic Statistics for Public Health (www.openepi.com). The results are summarized in Table 4 (also on the next page).

Table 3. Power for the proposed RCT on rESWT + RP for acute HMC injury Type 3b, accounting for a two sided-confidence interval of 95% and a percentage of patients with treatment success when treated with rESWT + RP of 75%. *, calculated from data reported by Reurink et al. (2014a) and Bayer et al. (2017).

Percent of patients treated with sham-rESWT + RP with treatment success [%]	Power based on Normal approximation [%]	Power based on Normal approximation with continuity correction [%]
99.9	67.4	44.8
90	23.4	10.3
80	5.3	5.3
70	5.0	5.0
60	16.9	8.0
50	36.8	23.6
40	61.7	47.1
30	84.1	73.2
25*	91.8	84.2
20	96.6	92.3
10	99.8	99.3
0	100	100

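### Randomizing at the first visit (D0–D2), before the arms differ on D5, leaves a gap in which a patient found ineligible must be kept or removed after allocation

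*Protocol*

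**What the plan says.** Protocol Section 4.9 places the first visit on the day of injury or one of the two days after it. Under the words "The Principal Investigator will perform the following procedures at the first visit" it lists the eligibility check, informed consent, randomization, and demographics with medical history. Until D5 every patient follows the same acute phase (rest, ice, compression, elevation). The arms first differ when "Study treatments (rESWT or sham-rESWT) will start on D5".

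Section 4.5 makes freedom from pain on the fifth day the condition for moving to the next rehabilitation phase. If symptoms last longer than five days, "we will reconsider the existence of more extensive tissue damage and/or intramuscular hematoma", with possible referral to an orthopedic surgeon. Section 4.3 admits only patients who do not need surgery. Section 4.4 excludes "Patients with clinical and ultrasonographic diagnosis of acute HMC injury Type 3A or Type 4".

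Three further rules bear on a patient whose ineligibility emerges after randomization:

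- Section 5 bases the main conclusions on intention to treat.
- Section 7.1 gives incorrect enrolment or randomization as a possible reason for withdrawal.
- Sections 5 and 7.3 forbid replacement once a patient has been randomized and has had the first session.

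On who knows the allocation, Section 4.8 has a medical assistant allocate by opaque sealed envelopes and keeps the assignment from health care staff during recruitment. The same section names the Principal Investigator as the unblinded therapist, and Section 4.9 lists the Principal Investigator as performing randomization. Section 4.11 states: "All assessments before the first treatment (baseline) and during the follow-up period will be performed by assessors blind to the intervention".

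**The concern.** Allocation comes 3 to 5 days before it has any effect on treatment (D5 minus D2, D5 minus D0). In that interval the protocol itself foresees new diagnostic information that can contradict the entry criteria, and its rules for such a patient pull in different directions. Intention to treat keeps the patient in the arm. The withdrawal rule lets the patient be taken out. The replacement rule, by barring replacement only after the first session, implies that a randomized but untreated patient may be replaced.

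Each route has a cost. A patient with a surgical injury who stays in is unlikely to return to play early in either arm, which shrinks the observed difference. A patient who is removed and replaced leaves the sample size intact, but the analysed set then depends on a judgement made after allocation. If the person making that judgement knows the arm, the removal can differ between arms. With 20 patients per arm, one or two such decisions matter.

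**Working it through.** **Timing and rules side by side**

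| Step | When | Source |
|---|---|---|
| Eligibility check, consent, randomization | D0–D2 | 4.9 |
| Same acute-phase care in both arms | to D5 | 4.5, 4.9 |
| Reconsideration of more extensive damage, if symptoms persist | after five days | 4.5 |
| First rESWT or sham session | D5 | 4.9 |
| Replacement barred | after the first session | 5, 7.3 |
| Latest permitted enrolment | seven days after injury | 4.4 |

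The last row shows that allocation on D5 is already compatible with the entry criteria.

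**Reproducing the stated power**

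Inputs from Section 5.1: n = 20 per arm, success 75% against 25%, two-sided 5% level. With d the difference and p̄ the mean of the two proportions,

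- power = Φ[(d − 1.96·s₀)/s₁], where s₀ = √(2p̄(1−p̄)/n) and s₁ = √((p₁(1−p₁)+p₂(1−p₂))/n).
- s₀ = √(0.5/20) = 0.1581 and s₁ = √(0.375/20) = 0.1369.
- Without continuity correction: (0.50 − 0.3099)/0.1369 = 1.39, power 91.7% (Table 3: 91.8%).
- Subtracting 1/n = 0.05 from d as a continuity correction: (0.45 − 0.3099)/0.1369 = 1.02, power 84.7% (Table 3: 84.2%).

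The plan's figures reproduce to within half a point.

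**Sensitivity to patients found ineligible after randomization**

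The protocol gives no rate, so k per arm is an assumption. If k patients per arm stay in and none returns by day 35, both proportions are multiplied by (1 − k/20). For k = 1 they are 71.25% and 23.75%, so s₀ = 0.1579, s₁ = 0.1389, and (0.475 − 0.3095)/0.1389 = 1.19, giving 88.3%. If instead these patients are lost and not replaced, n becomes 20 − k at unchanged proportions.

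| k per arm | Kept as failures: power / with correction | Lost, not replaced | Replaced |
|---|---|---|---|
| 0 | 91.7% / 84.7% | 91.7% / 84.7% | unchanged |
| 1 | 88.3% / 79.7% | 90.3% / 82.2% | unchanged |
| 2 | 84.4% / 74.3% | 88.5% / 79.3% | unchanged |
| 3 | 80.0% / 68.7% | 86.5% / 76.0% | unchanged |
| 4 | about 75% / 63% | 84.2% / 72.4% | unchanged |

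These figures concern the proportion returned by day 35. The planned primary test is Mann-Whitney on days to return to play. A simulation with 4,000 runs per k used normal log-times with SD 1, separated by 2 × 0.6745 = 1.349 SD so that 75% and 25% fall below day 35. Ineligible patients were ranked last. Power was about 98%, 96%, 93%, 86% and 76% for k = 0 to 4.

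**The case against.** Randomizing after consent and an eligibility check, then analysing by intention to treat, is an ordinary and valid design. Four further arguments favour the plan.

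- **Replacement.** Because replacement is barred only after the first session, a patient removed before D5 can by implication be replaced, and the stated power is then untouched. The schedule in Section 4.8 covers fifty patients for 40 places, which could serve as a reserve, although the protocol does not say so. This stands against any claim that power must fall. It does not answer the departure from intention to treat.
- **The D5 clause is not an eligibility check.** A reader might infer that D5 is a decisive second screening for Type 4 injury. Section 4.5 does not say that. The clause is conditional on persisting symptoms and mentions neither Type 4 nor eligibility; it also covers hematoma, which is no exclusion criterion. Ultrasound is done at the first visit, and Section 1 of the protocol calls Type 4 rare. This stands, and makes larger values of k pessimistic. Damage needing surgery would nevertheless contradict Section 4.3.
- **Knowledge of the arm.** A reader might infer that the Principal Investigator certainly knows the arm before D5 and that Section 4.11 is therefore breached. Section 4.8 gives allocation to a medical assistant and conceals it from staff, so early knowledge follows only from the task list in Section 4.9. The two sections conflict; the risk is real but not established.
- **Limits of a later allocation.** The clause speaks of more than five days, so some cases would surface after D5 whatever the timing. This also stands.

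**Conclusion.** The timing point holds as a weakness of design that is cheap to remove. Allocation on D0–D2 gains nothing evident from the protocol, because the arms are identical until D5. It opens an interval in which a patient can be found ineligible with no stated rule for what follows. Intention to treat, withdrawal and implied replacement then give different answers, and the choice may be made by someone who knows the arm.

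A reader might conclude that the trial is underpowered or that Table 3 is wrong. Neither follows. The stated 91.8%/84.2% is correct for its inputs. A loss arises only if ineligible patients are kept, or are lost without replacement. With 1 or 2 per arm kept as failures, power on the day-35 proportion would be about 88%/80% or 84%/74%, and for the Mann-Whitney test about 96% or 93% under the simulated distribution. These figures rest on an assumed rate and on none of these patients returning by day 35. They are a sensitivity range and not a forecast.

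**What to change.** In Section 4.9, keep consent, the first eligibility check and the collection of baseline data at D0–D2. Move randomization to D5: reconfirm the existing criteria of Sections 4.3 and 4.4, then have the medical assistant open the envelope immediately before the first session. Remove randomization from the Principal Investigator's task list so that Sections 4.8 and 4.9 agree. Count the 20 + 20 from patients confirmed eligible on D5, and keep D0 as the start of the return-to-play clock. The pain-free condition in Section 4.5 governs progression in rehabilitation and should not become a new entry criterion, since that would change the study population.

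The cost is a few lines of text and a later envelope opening at a visit already scheduled. A few consented patients will not be randomized and should appear in the screening log. The change does not cover damage recognised after D5; those patients stay in the intention-to-treat analysis. Nor does it solve a separate problem: Section 4.9 has the unblinded Principal Investigator perform efficacy assessments at all visits, which has to be reconciled with Section 4.11 in its own right.

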4.8. Randomization and blinding of patients

- Patients that fulfill the inclusion criteria and do not fulfill any of the exclusion criteria will be randomly allocated to either rESWT + RP (n=20) or sham-rESWT + RP (n=20).
- Randomization will be performed as described by Rompe et al. (2008) in a randomized, controlled study on rESWT for Achilles tendinopathy. Specifically, a computerized random-number generator will be used to formulate an allocation schedule. Patients will be randomized to either treatment (rESWT + RP or sham-rESWT + RP), with use of the method of randomly permuted blocks. The randomization scheme will be generated with the use of the website, www.randomization.com. Fifty patients will be randomized into five blocks. A medical assistant at the clinic of the Principal Investigator will allocate interventions by means of opaque sealed envelopes that will be marked according to the allocation schedule. The medical assistant will be unaware of the size of the blocks.

- The randomized intervention assignment as outlined above will be concealed from both patients and health care staff until recruitment will be complete and irrevocable.
- Patients will be blinded in this study.
- The assessor will be blinded in this study. The assessor is the person who will assess the outcome of treatment during follow up. In this study, the assessor will be a medical assistant at the clinic of the Principal Investigator.
- The therapist will not be blinded in this study. The therapist is the person who will administer either rESWT or sham-rESWT to the patient. In this study, the therapist will be the Principal Investigator ([name]).

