- perform clinical examination
- perform physical examination of the injured muscle
- dispense study treatment
- perform efficacy assessment
- report adverse events (AE) and serious adverse events (SAE)
- complete relevant section of case report form (CRF)

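### Protocol 4.9 gives efficacy assessment at every visit to the unblinded Principal Investigator, against the blinded-assessor rule in 4.2, 4.8 and 4.11

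*Protocol*

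**What the plan says.** **Who assesses outcome, according to the blinding text.** Section 4.2 describes a trial with blinded patients and evaluators and unblinded therapists. Section 4.8 defines the roles by function: "The assessor is the person who will assess the outcome of treatment during follow up". That person is blinded and is a medical assistant at the clinic. For the other role, "In this study, the therapist will be the Principal Investigator", and the therapist is not blinded. Section 4.11 gives every baseline and follow-up assessment to assessors who do not know the allocation. Section 5 refers follow-up to section 4.10, where return to play is defined. Section 4.1 claims the PEDro items, assessor blinding among them, with therapist blinding as the only exception.

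**Who assesses outcome, according to the visit text.** Section 4.9 says "Furthermore, the Principal Investigator will perform the following procedures at all visits". The list includes "perform physical examination of the injured muscle", "dispense study treatment", "perform efficacy assessment" and completion of the matching case report form section.

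**What is assessed.** Under 4.10.1 the primary outcome is the number of days to return to play, which requires seven criteria. The last is clearance by medical staff, a term that neither 4.5 nor 4.10.1 defines. Neither place requires the person giving clearance to be unaware of allocation.

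**The concern.** The person told in 4.9 to assess efficacy at each visit is the one person the protocol declares unblinded. The same list has that person give the treatment, so it cannot be read as the blinded assistant's task list.

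All seven criteria must be met before a return-to-play day is counted, so a single staff-judged criterion can move the date. If 4.9 is followed for the primary outcome, a significant Mann-Whitney result would be open to the assessment bias that the blinded-assessor rule exists to exclude. No later analysis could remove that doubt. What patients report about pain and confidence is protected for as long as the sham handpiece keeps them blind.

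**Working it through.** **Step 1: the texts side by side.**

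| Question | 4.2, 4.8, 4.11 | 4.9 |
|---|---|---|
| Who assesses outcome? | Blinded assessor, a medical assistant | Principal Investigator |
| Does that person know the allocation? | No | Yes: the therapist under 4.8 |
| When? | Baseline and follow-up, all assessments | All visits |

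No section limits the 4.9 list, passes its efficacy item to the assistant, or gives one section precedence. Section 4.5 bars the rehabilitation physiotherapist from any later evaluation of the patient. No such bar is stated for the Principal Investigator.

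**Step 2: how literally 4.9 can be read.** The list has treatment given at all visits, yet the same section says "Each subject will be treated with nine sessions of rESWT or sham-rESWT, with three sessions per week", with example days from D5 to D23. It also plans a six-month visit for satisfaction only. The list is therefore partly generic, and it does not prove that the Principal Investigator will set the return-to-play date.

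**Step 3: the criteria in 4.10.1.** Four concern pain (palpation, flexibility, strength and functional tests) and one concerns confidence: 4 + 1 = 5 that rest on what a blinded patient reports. Two are judged by staff: comparable hamstring flexibility, with no threshold given there, and clearance. Total 5 + 2 = 7. The split is approximate, because an examiner elicits and interprets some of the pain findings.

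**Step 4: the protocol's own figures.** Section 4.9 expects 75% and 25% of patients to return within five weeks of D0. With 20 per arm that is 0.75 × 20 + 0.25 × 20 = 15 + 5 = 20 of 40 dates, at a time when patients attend three times a week. The power in Table 3 reproduces. With n = 20, the standard error under the null is √(2 × 0.5 × 0.5/20) = 0.158 and under the alternative √(2 × 0.1875/20) = 0.137. Then Φ((0.50 − 1.96 × 0.158)/0.137) = 91.7%, against 91.8% stated. The concern disputes no figure in the plan.

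**Step 5: illustration of possible size.** Medians, log-SDs and shifts are assumptions. The set-up is 20 per arm, no true effect, lognormal times rounded up to whole days, two-sided asymptotic Mann-Whitney at 0.05 with tie and continuity correction, and 20,000 replicates per scenario.

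- (a) Median 46 days, log-SD 0.4, chosen so that about 25% return by day 35: Φ(ln(35/46)/0.4) = 24.7%.
- (b) Median 62.5 days, log-SD 0.35, matching the early-rehabilitation arm shown in Figure 6 and the 5% by day 35 in section 5.1: Φ(ln(35/62.5)/0.35) = 4.9%.

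False-positive rate (%) by the number of days that rESWT patients are cleared early:

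| Share cleared early | Scenario | 0 | 2 | 3 | 5 | 7 | 10 |
|---|---|---|---|---|---|---|---|
| All | a | 4.8 | 6.2 | 7.9 | 13.3 | 21.8 | 38.7 |
| All | b | 4.7 | 5.6 | 6.6 | 10.5 | 16.3 | 28.9 |
| Half | a | 4.8 | 5.1 | 5.5 | 6.9 | 8.6 | 12.3 |
| Half | b | 4.7 | 5.0 | 5.2 | 6.0 | 7.3 | 10.0 |
| Quarter | a | 4.8 | 4.9 | 5.0 | 5.4 | 5.8 | 6.5 |
| Quarter | b | 4.7 | 4.7 | 4.8 | 5.0 | 5.3 | 5.7 |

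Repeat runs with other seeds differed by at most about 0.6 percentage points. By D23 only Φ(ln(23/46)/0.4) = 4.2% (a) or Φ(ln(23/62.5)/0.35) = 0.2% (b) have returned. The visits that matter for the date therefore come mostly after the treatment sessions.

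**The case against.** The best defence is that the design is already fixed. Blinded assessment is stated in three sections, two of them devoted to blinding, while 4.9 is a visit checklist with generic items. It never says that the Principal Investigator's assessment is the primary outcome or replaces the assessor's. A treating clinician may check progress while the assistant records the endpoint. On that reading the rule in 4.11 also covers clearance and need not be repeated beside each criterion.

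Part of this stands. The 4.9 list does not show that unblinded assessment is intended. Nothing identifies the medical staff who give clearance as the Principal Investigator. The count of 20 of 40 is only background, because clinic visits continue beyond week five. The 5-to-2 split does not measure exposure. The simulated inflation is small unless early clearance is both widespread and large.

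What does not stand is that the contradiction resolves itself. Section 4.11 speaks of assessors, clearance belongs to undefined medical staff, and 4.9 gives an explicit contrary instruction with no limit. Staff who followed 4.9 to the letter would be complying with one section of the protocol while breaking another.

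**Conclusion.** The concern holds. The protocol gives two incompatible instructions on who assesses efficacy, one of them to the unblinded therapist, and does not say which governs. The clearance that completes the primary outcome has no blinding condition of its own. This is wrong as written rather than detail left for later, and it should be corrected.

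The size of any bias is unknown. Under the assumed scenarios, a one-visit shift in every rESWT patient gives a false-positive rate of 5.6% to 7.9%. The same shift in half of them gives 5.0% to 5.5%, and in a quarter it stays near 5%. A 7-day shift in every patient gives 16% to 22%. The conclusion depends on the conflict between sections 4.9 and 4.2, 4.8 and 4.11, not on these figures.

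**What to change.** Reconcile 4.9 with 4.2, 4.8 and 4.11:

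1. Remove the efficacy assessment from the Principal Investigator's list.
2. State that the Principal Investigator's clinical and muscle examinations serve treatment delivery and safety and do not feed the primary outcome.
3. State that the blinded assessor named in 4.8 performs the return-to-play tests, records the date and completes that part of the case report form.
4. State that the clearance counted in the primary outcome is given by someone unaware of allocation.

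Two related clarifications can be made in the same edit, although the finding does not rest on them. Say that the assistant who allocates by envelope is not the assessor. Also reconcile randomization by the Principal Investigator in 4.9 with allocation by the assistant in 4.8.

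The cost is wording and delegation of tasks, with no change to sample size, endpoint or test. In practice the assessor must be available whenever return to play is tested, and whoever gives the counted clearance must be kept unaware of allocation.
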